13.5 Analysis Populations

Cases withdrawn prior to the Pure-Vu procedure and those with technical failures will be excluded from the primary analysis. Cases with failure to reach the desired colon segment per the intended indication, which cannot be conducted with Pure-Vu, will be excluded from the primary analysis. All subjects who have the Pure-Vu inserted will be included in the safety analysis.

Individual listings of withdrawal / technical failure including descriptive information will be provided.

Document Title:	Document No.	Version	Page 30 of 44
Evaluation of the bowel cleansing in hospitalized population using Pure-Vu System	CL00044	4.0	

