6.3 Clinical data to Date

The Pure-Vu System was evaluated in ninety-seven subjects (54% males) from five sites using similar protocol.

Pure-Vu was used in subjects indicated for a screening, diagnostic or surveillance colonoscopy. To ensure an inadequately prepped colon, subjects underwent a reduced preparation consisting of dietary restrictions (no dried fruit, seeds or nuts) starting 2 days prior to the colonoscopy, an 18 to 24 hour clear liquid diet and a split dose of 20mg Bisacodyl.

The cleansing quality was evaluated before and after use of the Pure-Vu System with the Boston Bowel Preparation Score (BBPS) (1).

Two subjects were excluded from the analysis due to the followings: One subject had breakfast on day of procedure and therefore was excluded from the cleansing efficacy and usability analysis due to non-compliance with the pre-procedural prep regimen. The other subject was excluded because the device could not reach beyond the sigmoid colon due to the subject's

Document Title: Evaluation of the bowel cleansing in hospitalized population using Pure-Vu System	Document No. CL00044	Version 4.0	Page 17 of 44
---	--------------------------------	-----------------------	---------------

anatomy, thus the physician used a slim colonoscope to complete the procedure and indicated that only a slim colonoscope would be able to advance past the sigmoid and into the cecum.

The Pure-Vu significantly increased the number of subjects with an adequate cleansing level (BBPS ≥ 2 for all 3 colon segments) from 25%; CI 95% [17%, 35%] at baseline to 99%; CI 95% [94%, 100%] after Pure-Vu. Cecum intubation rate was 98%; CI 95% [94%, 100%]). Mean post-treatment BBPS score was 8.7 ± 1.0 vs. 3.9 ± 2.2 prior to Pure-Vu use. Physicians were satisfied with the device's use. No major difficulties were experienced when performing polypectomy and no serious adverse events were reported.

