13.2 Description of statistical methods

Basic demographic and other baseline characteristics will be collected and analyzed for all subjects. Summary statistics (mean, standard deviation, median, minimum and maximum for quantitative variables) will be presented for the total study population. Frequency tables for qualitative data will be provided.

Any deviation from specified statistical plan will be in addition to “per protocol” analysis and will be reported as such. Intent-To-Treat and Post-hoc analysis will be conducted according to the existing data gathered, if necessary.

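### The primary improvement rate leaves out technical and reach failures with no committed rate in all subjects with Pure-Vu inserted, and the definition of first-attempt success differs between sections

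*Combined protocol and SAP*

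**What the plan says.** **Analysis set.** Section 13.5 has two exclusion rules for the primary analysis. The first is: "Cases withdrawn prior to the Pure-Vu procedure and those with technical failures will be excluded from the primary analysis". The second is: "Cases with failure to reach the desired colon segment per the intended indication, which cannot be conducted with Pure-Vu, will be excluded" from the same analysis. For safety it uses a wider set: "All subjects who have the Pure-Vu inserted will be included in the safety analysis". Section 13.4.1 describes the safety set differently, as all enrolled subjects, and section 12.3 counts a subject as enrolled once consent is signed.

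**Basis of the rate.** Section 13.3 commits to counts and percentages of improved segments and improved subjects, with 95% confidence intervals. It bases the primary assessment on every colon segment seen during the examination.

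**Other outputs that touch on the exclusions.** Section 13.5 adds: "Individual listings of withdrawal / technical failure including descriptive information will be provided". Reach failures are not named there. Section 13.4.2 reports cecal intubation with Pure-Vu. Section 13.2 says: "Intent-To-Treat and Post-hoc analysis will be conducted according to the existing data gathered, if necessary". It names no analysis set and gives no rule for scoring failures.

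**First-attempt success.** Section 9.2 specifies that the successful colonoscopy is one with Pure-Vu. The synopsis and the definition in section 13.4.2 lack that qualifier. Section 12.5 provides for carrying on with another colonoscope, without Pure-Vu, when the cecum is not reached. Section 13.4.2 compares the first-attempt proportion with the one physicians would have expected had the device not been available.

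**The concern.** A technical failure after insertion, or a failure to reach the needed segment with the device fitted, is something that happens because the device was used. Removing such cases gives the improvement rate where the device worked and reached its target. A reader interested in what to expect when the device is inserted needs the other rate as well, and the plan does not commit to it.

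Sections 13.3 and 13.5 also pull apart. A subject whose descending segment was scored before and after cleansing, but whose ascending segment was never reached, contributes an observed segment under section 13.3. If that ascending segment was the one needed, section 13.5 drops the whole case.

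For first-attempt success, the question is whether an examination finished without Pure-Vu may count on the Pure-Vu side of the with-versus-without comparison. Section 9.2 says it may not. The wording in section 13.4.2, which governs the analysis, does not settle it.

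**Working it through.** **1. The plan's own earlier figure.** Section 6.3 reports 97 earlier subjects, two of them excluded, leaving 95. One had not complied with preparation. On the other it says: "The other subject was excluded because the device could not reach beyond the sigmoid colon". With counts inferred from the rounded percentages, exact 95% intervals reproduce the reported adequacy rates:
- baseline: 24/95 = 25.3% (16.9 to 35.2), against the reported 25% (17 to 35)
- after use: 94/95 = 98.9% (94.3 to 100.0), against the reported 99% (94 to 100)

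Counting the reach failure as not adequate gives 94/96 = 97.9% (92.7 to 99.7), a drop of about 1 point. This is adequacy per subject, not improvement per segment, but the mechanism is the same.

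**2. General formula.** Let f be the share of segments excluded, p the improvement rate in analysed cases and q the rate in excluded cases. The rate with everyone counted is (1 − f)p + fq, so

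overstatement = p − [(1 − f)p + fq] = f(p − q).

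**3. Inputs.** None of f, p or q is given for this trial.
- f: section 6.3 offers two nearby anchors. One is the single reach failure among 97 − 1 = 96 preparation-compliant subjects: 1/96 = 1.0% (exact interval 0.0 to 5.7). The other is "Cecum intubation rate was 98%; CI 95% [94%, 100" percent], that is, about 2% not reached and 6% at the unfavourable limit. No count is given behind that 98%. Exact intervals for 94/96 or 95/97 start at 92.7%, so the printed limit is used as it stands. Neither anchor is the same as missing the segment needed for the indication, and neither counts technical failures separately. The 5% row is an assumption.
- p: 50–99%, an assumption. A segment already at BBPS 3 cannot improve, and these subjects receive standard preparation rather than the reduced preparation of the earlier study.
- q: 0 is the worst case. One third corresponds to one of three segments in an excluded case being reached and improved.

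**4. Overstatement in percentage points.**

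| f | q | p = 50% | p = 75% | p = 99% |
|---|---|---|---|---|
| 1% | 0 | 0.50 | 0.75 | 0.99 |
| 2% | 0 | 1.00 | 1.50 | 1.98 |
| 5% | 0 | 2.50 | 3.75 | 4.95 |
| 6% | 0 | 3.00 | 4.50 | 5.94 |
| 1% | 1/3 | 0.17 | 0.42 | 0.66 |
| 2% | 1/3 | 0.33 | 0.83 | 1.31 |
| 5% | 1/3 | 0.83 | 2.08 | 3.28 |
| any | = p | 0 | 0 | 0 |

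**5. Example in counts.** Take 100 subjects with three segments each, two subjects excluded, q = 0. Then 147/294 = 50.0% becomes 147/300 = 49.0%, and 291/294 = 99.0% becomes 291/300 = 97.0%. No binomial interval is shown per segment, because segments cluster within subjects.

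**6. First-attempt success.** The two wordings differ by 1 point for each 1% of subjects finished successfully without Pure-Vu. Section 6.3 shows that this can happen: "thus the physician used a slim colonoscope to complete the procedure". At the earlier 1/96 the difference is about 1 point. It is zero if no examination is switched.

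**The case against.** The strongest reply is that the primary objective concerns cleansing, not access. A segment that was never reached has no score before or after use, so section 13.3 reasonably restricts itself to what was observed. The study is a single-arm pilot with no sample-size basis and no success threshold, and on the protocol's own anchors the shift is a point or two. Failures are also partly visible: cecal intubation with the device is a committed endpoint with an interval, technical failures are listed individually, and section 14.9 requires device deficiencies to be documented. Some technical faults would be found at the check before insertion and would not enter an all-inserted rate.

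Much of this stands. The conditional rate is a fair question and should stay, and the effect is probably small. The disclosures do not complete the picture, however. Cecal intubation measures reach rather than improvement, the listing does not name reach failures, and the plan does not say whether a technical failure means the same as a device deficiency.

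Three stronger readings are tempting but not supported:
- *The all-inserted rate cannot be obtained from the planned outputs.* Section 13.3 commits to the count of improved subjects. If the number inserted is reported, dividing one by the other gives the worst-case (q = 0) rate per subject. What is missing is a planned, labelled rate and the scored segments of excluded cases.
- *The overstatement is large.* Exclusion rates of 10% or more have no source in the documents.
- *Section 13.4.2 credits examinations finished without the device.* It requires the procedure to go as scheduled, and section 10 schedules colonoscopy with Pure-Vu. It also contrasts the result with absence of the device. The text leaves the matter open; it does not decide it in the device's favour.

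**Conclusion.** The point holds as a minor to moderate one. The primary rate is conditional on the device working and reaching the needed segment, and it will tend to overstate the rate in all subjects with the device inserted. On the anchors in section 6.3 the overstatement is about 0.5–2 points if excluded cases count as not improved, 0.2–1.3 points if a third of their segments improved, and nothing if they improved as often as the rest. It reaches 3.0–5.9 points only at the unfavourable limit of the reported cecal interval. These figures rest on an assumed p of 50–99% and on exclusion rates borrowed from an earlier study with a different preparation; this trial's rate is unknown.

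The mismatch in first-attempt success is a plain inconsistency, worth about 1 point at the earlier frequency. Neither issue undermines the study. Both are better settled before the data are seen than under an optional intent-to-treat clause afterwards.

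**What to change.** **In section 13.5:**
- Keep the current analysis. Add a committed supportive analysis of the improvement rate, per subject and per segment, in all subjects with Pure-Vu inserted.
- In it, observed segments keep their BBPS. Segments required by the indication but not reached with Pure-Vu, or lost to a technical failure after insertion, count as not improved. State this as an imputation rule.
- Say how a subject with a mixture of improved and unreached segments is classified, since section 13.3 does not say how many segments must improve.
- Report the numbers excluded by reason, with reach failures named, beside the number inserted. Say what counts as a technical failure.
- Define the inserted set explicitly and reconcile the safety set between section 13.4.1 (all enrolled) and section 13.5 (all inserted).

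**In the synopsis and section 13.4.2:** adopt the section 9.2 qualifier for first-attempt success. Examinations finished without Pure-Vu under section 12.5 are then not counted as device successes in the comparison. List them separately.

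**Cost:** wording in three or four places, one extra table and a fuller listing. The CRF must show which segments the indication required, which were reached with the device, and whether the examination was finished without it. The rates will look slightly less favourable, and the supportive rate mixes access with cleansing, which is why it sits beside the current analysis and does not replace it.

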13.6 Interim Analyses

An interim analysis is planned after procedure completion of 45 subjects aims to verify the recruitment pace and the study flow.

14.0 Adverse Events (AEs) and Complications

AE and AE subcategies are defined per ISO14155:2011, as described below.

14.1 Adverse Event (AE)

An AE is any untoward medical occurrence, unintended disease or injury, or untoward clinical signs (including abnormal laboratory findings) in subjects, whether or not related to the investigational medical device.

This definition includes events related to the investigational medical device or the comparator and the procedures involved.

AEs will be collected starting from the time subject is enrolled until the follow-up period is completed.

14.2 Serious Adverse Event (SAE)

A Serious AE (SAE) is an AE that has

- a) Led to death,
- b) Led to serious deterioration in the health of the subject, that either resulted in
 - 1) A life-threatening illness or injury, or
 - 2) A permanent impairment of a body structure or a body function, or
 - 3) In-patient or prolonged hospitalization, or
 - 4) Medical or surgical intervention to prevent life-threatening illness or injury or permanent impairment to a body structure or a body function,

Document Title: Evaluation of the bowel cleansing in hospitalized population using Pure-Vu System	Document No. CL00044	Version 4.0	Page 31 of 44
---	--------------------------------	-----------------------	---------------

c) Led to fetal distress, fetal death or a congenital abnormality or birth defect

NOTE: Planned hospitalization for a pre-existing condition, or a procedure required by the clinical investigational plan, without serious deterioration in health, is not considered an SAE.

Some important medical events, although they may not result in death, be life-threatening, or require hospitalization may still be considered SAEs when, based upon appropriate medical judgment, they are felt to jeopardize the subject and may require medical or surgical intervention to prevent one of the outcomes listed above.

Life threatening means that the subject was, in the view of the investigator, at immediate risk of death from the reaction as it occurred. This does not include an AE that, if more severe, might have caused death.

Disability means a substantial disruption of a person's ability to conduct normal life's functions.

14.3 Adverse Device Effect (ADE)

An Adverse Device Effect (ADE) is an AE related to the use of an investigational medical device. This definition includes AEs resulting from insufficient or inadequate instructions for use, deployment, implantation, installation, or operation, or any malfunction of the investigational medical device.

This definition includes any event resulting from use error or from intentional misuse of the investigational medical device.

14.4 Serious Adverse Device Effect (SADE)

A Serious Adverse Device Effect is an adverse device effect that has resulted in any of the consequences characteristic of an SAE.

Document Title: Evaluation of the bowel cleansing in hospitalized population using Pure-Vu System	Document No. CL00044	Version 4.0	Page 32 of 44
---	--------------------------------	-----------------------	---------------

14.5 Unanticipated Serious Adverse Device Effect (USADE)

An Unanticipated Serious Adverse Device Effect is a serious adverse device effect which by its nature, incidence, severity, or outcome has not been identified in the current version of the risk analysis report.

14.6 Adverse Event Severity Classification

Severity will be defined according to the following criteria:

Mild	Awareness of event, but easily tolerated
Moderate	Discomfort enough to cause some interference with activities of daily living (ADL)
Severe	Incapacitating, with an inability to perform ADL

An AE can be classified as severe and not deemed a SAE. Similarly, a SAE is not automatically severe in nature.

14.7 Adverse Event Relationship Classification

Relationship to study product administration will be determined as follows:

- *No Relationship:* No relationship between the AE and the administration of study treatment and a known relationship to other etiologies such as concomitant medications, procedure, or subject's clinical state.
- *Possible Relationship:* An AE that follows a reasonable temporal sequence from administration of the study treatment and follows a known response pattern to the study treatment but could have been produced by the participant's clinical state or by other therapies.
- *Probable Relationship:* An AE that follows a reasonable temporal sequence from administration of the study treatment; follows a known response pattern to the study treatment; and cannot be reasonably explained by the known characteristics of the participant's clinical state or by other therapies.

Document Title:	Document No.	Version	Page 33 of 44
Evaluation of the bowel cleansing in hospitalized population using Pure-Vu System	CL00044	4.0	

- *Definite Relationship*: An AE that follows a plausible temporal sequence from administration of the study treatment and follows a known response pattern to the study treatment. The reaction cannot be reasonably explained by the known characteristics of the subject's clinical state or other modes of therapy administered to the subject.
- *Unknown/Impossible to Determine*: Given the information available, sequence and timing of events, it is unknown or impossible to determine the relationship of the AE with the study treatment.

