13.4 Secondary Endpoints Analysis

13.4.1 Safety Analysis

The secondary endpoint is to evaluate the device related adverse event and the overall adverse events rate. The safety analysis set will consist of all subjects who were enrolled into the study.

Document Title: Evaluation of the bowel cleansing in hospitalized population using Pure-Vu System	Document No. CL00044	Version 4.0	Page 29 of 44
---	--------------------------------	-----------------------	---------------

Individual listings of adverse events including type, reported term, seriousness, duration, relationship to the study device, severity and the adverse events outcome will be provided for the total population. AEs will be summarized using frequency counts and percentages.

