14.10 Adverse Event Recording and Reporting

Assessment of the occurrence of an AE will be based on changes in the subject's signs and symptoms. AEs will be monitored until a subject completes the study unless the Investigator determines the event is related to the investigational device, in which case they will be monitored until resolution if possible. Medical care will be provided, as defined in the informed consent, for any AE related to study participation. AEs will be collected on an AE CRF and applicable source documentation.

The following should not be considered an AE:

- A condition requiring a preplanned procedure unless the condition worsened since screening
- A preexisting condition found as a result of screening, unless the condition has worsened since enrollment.

All AEs observed during the course of this study, regardless of severity or relationship to the investigational device will be recorded on the appropriate CRF.

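### Section 14.7 has no related category for a device effect that is new in nature, so the device-related AE rate may be understated

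*Combined protocol and SAP*

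**What the plan says.** Section 14.7 rates the relationship of an AE to the study treatment in five categories:

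- **No Relationship** requires no link to the treatment "and a known relationship to other etiologies such as concomitant medications, procedure, or subject's clinical state".
- **Possible** requires a reasonable time sequence "and follows a known response pattern to the study treatment but could have been produced by" the patient's condition or other therapies.
- **Probable** requires that the event "follows a known response pattern to the study treatment; and cannot be reasonably explained by the known characteristics" of the patient's condition or by other therapies.
- **Definite** requires a plausible time sequence "and follows a known response pattern to the study treatment. The reaction cannot be reasonably explained" by the patient's condition or other treatment.
- **Unknown/Impossible to Determine** applies when "it is unknown or impossible to determine the relationship of the AE with the study treatment".

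Four other places bear on this:

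- **14.3** defines an adverse device effect (ADE) as an AE related to use of the device. It sets no pattern condition, and it includes effects of malfunction, inadequate instructions and use error.
- **14.5** defines an unanticipated serious adverse device effect (USADE) as one that by nature, incidence, severity or outcome "has not been identified in the current version of the risk analysis report".
- **13.4.1** states: "The secondary endpoint is to evaluate the device related adverse event and the overall adverse events rate". It does not say which 14.7 categories count as device related or how Unknown is treated.
- **14.10** limits AE monitoring to the time in the study, with one exception: "unless the Investigator determines the event is related to the investigational device, in which case they will be monitored until resolution if possible".

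**The concern.** A relationship scale should let an investigator record a suspected device effect whether or not it has been seen before. Here every category that expresses suspicion presupposes a pattern that is already known. An effect of a new kind has no such pattern, so the investigator who follows 14.7 has only Unknown left.

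Three things depend on the rating. The device-related AE rate is half of the safety endpoint in 13.4.1, and device safety is a secondary objective in 8.2. Monitoring to resolution in 14.10 is reserved for related events; for others, monitoring ends with study participation, which section 11.0 puts at about 3 days. Under 14.11 a non-serious event is reportable as an ADE only if it is held to be related. If events are misplaced in this way, the device-related rate can only move in the device's favour.

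**Working it through.** **Text check.** Take an AE caused by the device, of a kind not seen before, and test it against 14.7.

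| Category | Required element | Can a device effect new in nature meet it? |
|---|---|---|
| No Relationship | Known link to another cause | No |
| Possible | Known response pattern | No |
| Probable | Known response pattern | No |
| Definite | Known response pattern | No |
| Unknown | Relationship cannot be determined | Only category left |

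The pattern condition is an added requirement in all three related categories, not an alternative. Three of three therefore exclude the event.

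Set this beside 14.3 and 14.5. A USADE must first be a device effect, which under 14.3 means an AE related to device use. Section 14.5 expects that some of these will be new by nature. Section 14.7, the only graded scale in the protocol for relationship, has no related category for them. The protocol does not say which text governs.

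**Which events are affected.** Section 14.5 lists four ways to be unanticipated. Unexpected incidence, severity or outcome of a known type of event can still satisfy a known pattern. Only the first way, nature, is shut out.

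**Size.** The plan states no figure that depends on this point, so there is none to reproduce. The following is an illustration.

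- Inputs: n = 100, the planned maximum (13.1); k = number of subjects with a device effect of a new kind (assumed); no other device-related AEs; Unknown not counted as related (assumed, because 13.4.1 is silent).
- Change in the rate: k/n, so one subject is 1/100 = 1 percentage point.
- Exact (Clopper-Pearson) 95% limits for x of n: lower = 2.5% quantile of Beta(x, n − x + 1), upper = 97.5% quantile of Beta(x + 1, n − x). For x = 0 the lower limit is 0 and the upper is 1 − 0.025^(1/n) = 1 − 0.025^(1/100) = 3.6%.

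| k | Rate if counted as related (95% CI) | Rate if left in Unknown (95% CI) |
|---|---|---|
| 1 | 1% (0.03-5.4%) | 0% (0-3.6%) |
| 2 | 2% (0.2-7.0%) | 0% (0-3.6%) |
| 5 | 5% (1.6-11.3%) | 0% (0-3.6%) |

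If k = 0, or if Unknown is counted as related, there is no understatement.

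**The case against.** The case on the other side is substantial, and most of it limits the point without removing it.

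- **Reach.** A reader might infer that no USADE could ever be rated related. The documents do not support that. Section 7.1 names perforation, pain, infection and bleeding as risks, so an unexpectedly severe or frequent event of those types could be a USADE and still fit a known pattern. This stands, and it confines the point to effects new in nature.
- **Different yardsticks.** Section 14.5 refers to the risk analysis report, whereas 14.7 leaves the known pattern undefined. An effect missing from the report could still follow a pattern familiar from colonoscopy. This stands too, but it does not help an effect that is new altogether.
- **Which text governs.** Section 14.3 does not refer to 14.7, and 14.10 rests on the investigator's determination, not on a named category. An investigator could therefore call a new effect related despite 14.7. That is possible, but it leaves two texts giving different answers.
- **Safeguards.** Section 14.10 has all AEs recorded whatever their relationship, 13.4.1 lists each one with its relationship and also gives the overall rate, and 14.11 has SAEs reported regardless of relationship. This stands in full. No event disappears, and a serious one is still reported.
- **Earlier experience.** It is tempting to argue that, with no SAE in 97 earlier subjects (exact 95% upper limit 1 − 0.025^(1/97) = 3.7%), any serious effect not yet seen would fail the known-pattern test. Section 7.1 contradicts this: it names perforation as a risk although no SAE occurred. That limit concerns how often SAEs occur, not which types are known.
- **Study type.** This is a pilot with a descriptive safety endpoint. That lowers the stakes, but the device-related rate is still a stated result.

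**Conclusion.** The point holds for device effects that are new in nature. As written, 14.7 gives them no related rating, which conflicts with 14.3 and 14.5. This is a stated rule that misclassifies, not a missing detail.

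The consequence is a risk, not a demonstrated result. The device-related AE rate may be understated, and such events may miss monitoring to resolution and, if non-serious, ADE reporting. A reader might infer that the rate will be understated; that would need three things the documents do not establish: such an event occurs, the investigator applies 14.7 literally, and the analysis leaves Unknown out of the device-related count. If all three hold, the cost is 1 percentage point per affected subject at n = 100. Events of known type with unexpected incidence, severity or outcome, the overall AE rate, the AE listings and SAE reporting are not affected.

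**What to change.** 1. In 14.7, remove the known-pattern condition from Possible. In Probable and Definite, change it to *known response pattern or otherwise plausible for the device*. The scale then agrees with 14.3 and 14.5. Because a new effect can then be rated related, the monitoring rule in 14.10 and ADE reporting in 14.11 can apply to it.
2. In 13.4.1, state that Possible, Probable and Definite count as device related, and show the rate with Unknown added beside it as a sensitivity count.

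Unknown is better kept out of the main rate. In acutely ill inpatients it could attribute unexplained background events to the device, and counting it in 13.4.1 would not by itself bring those events under 14.10.

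The cost is protocol wording and a CRF instruction. The downside is that the stated device-related rate may be slightly less favourable.
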